### 10.3.1 Reporting Period

The reporting period for all non-serious AEs and all SAEs not related to protocol procedures begins upon receiving the first dose of study medication and ends at the final protocol-required visit.

**SAEs that are assessed by the investigator to be related to protocol procedures (eg, ESA washout) must be reported after signing of the informed consent form.**

In addition, SAEs that occur after the protocol-defined AE reporting period that are considered to be related to the study medication should be recorded and reported to the sponsor's medical monitor or CRO designee.

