### **11.4 Study Populations**

#### **11.4.1 Analysis Population for the Safety Analyses**

The safety population is defined as all enrolled subjects who receive at least 1 dose of study medication. The safety population will be based on the actual treatment that patients received. All safety analyses will be performed using the safety population.

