## 12 DATA HANDLING AND RECORD KEEPING

### 12.1 Case Report Forms (CRFs)

This study will utilize an EDC system to manage data collection during this trial. The system is fully Code of Federal Regulations 21 part 11 compliant. An EDC system contains certain functionality including, but not limited to, a graphical user interface to help facilitate data entry, a data validation element to check user data, and a reporting function to assist with the review and analysis of data. CRFs available through this system are required and should be completed for each randomized subject.

Any form of data from the electronic system are the sole property of the sponsor and should not be made available in any form to third parties, except for authorized representatives of the sponsor or appropriate regulatory authorities, without written permission from the sponsor.

The investigator has ultimate responsibility for the accuracy, authenticity, and timely collection and reporting of all clinical, safety, and laboratory data entered in the EDC or any other data collection forms. The CRFs must be signed electronically by the Investigator to attest that the data contained on the CRFs is true.

In most cases, the source documents are contained in the subject's chart at the hospital or the physician's office. In these cases, data collected on the CRFs must match the data in those charts.

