4.4.1 Analysis Population for the Safety Analyses

The safety summaries and analyses will be based on the **safety population**. The safety population is defined as all enrolled subjects who receive at least 1 dose of study medication. In the event that a subject is allocated the incorrect study treatment as per the study randomization list, subjects will be summarized and analyzed ‘as treated’ i.e. by allocated treatment group.

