4.8 Safety Evaluation

All safety summaries and analyses will be based upon the safety population as defined in [Section 4.4](#).

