If the start and/or stop dates of medications other than study treatments are missing or partially missing, the dates will be compared as far as possible with the date of first study treatment administration.

If not specified, observed data approach will be performed.

The AE will be summarized using MedDRA system organ class (SOC) and preferred term (PT). All AE summaries will provide the number of subjects reporting at least one AE and the total number of events reported. The following summaries will be provided:

- A summary of the number and percentage of subjects reporting at least one TEAE, drug-related TEAE, TEAE leading to withdrawal, serious adverse event (SAE), drug-related SAE, SAE leading to withdrawal and death by treatment group.
- A summary of the number and percentage of subjects reporting a TEAE by treatment group, SOC, and PT

- A summary of the number and percentage of subjects reporting a drug-related TEAE by treatment group, SOC, and PT
- A summary of the number and percentage of subjects reporting a treatment-emergent SAE by treatment group, SOC, and PT
- A summary of the number and percentage of subjects reporting a SAE during the screening period Assessed as Related to Protocol Procedures by treatment group, SOC, and PT
- A summary of the number and percentage of subjects reporting a drug-related treatment-emergent SAE by treatment group, SOC, and PT
- A summary of the number and percentage of subjects reporting a drug-related TEAE leading to withdrawal by treatment group, SOC, and PT
- A summary of the number and percentage of subjects reporting a TEAE leading to withdrawal by treatment group, SOC, and PT
- A summary of the most common TEAEs by treatment group and PT (reported by >10% of subjects in any treatment group)
- A summary of the number and percentage of subjects reporting a TEAE by treatment group, severity, SOC, and PT
- A summary of the number and percentage of subjects reporting a TEAE by treatment group, relationship, SOC, and PT

AE summaries will be ordered alphabetically for SOC, and PT within SOC.

For each subject and each AE, the worst severity recorded will be attributed and used in the by-severity summaries. Similarly, the worst causality (most related to treatment) will be attributed and used in the by-causality summaries. If severity or causality is missing, data will be treated as observed.

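### The table of procedure-related screening SAEs is confined to dosed subjects by treatment group, so an event in anyone not randomised cannot appear in it

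*SAP*

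**What the plan says.** **Collection.** Protocol 10.3.1 starts most AE reporting at the first dose. SAEs that the investigator relates to protocol procedures, with ESA washout as the example, "must be reported after signing of the informed consent form". The Protocol's summary of changes explains why: screening withdraws ESAs from patients who are using them.

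**Tabulation.** SAP 4.8.2 plans counts and percentages, broken down by MedDRA class and term, for those "reporting a SAE during the screening period Assessed as Related to Protocol Procedures by treatment group". A closing sentence in the same section keeps these events apart from treatment-emergent SAEs.

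**Population.** SAP 4.8 states: "All safety summaries and analyses will be based upon the safety population". SAP 4.4.1 defines that population as "all enrolled subjects who receive at least 1 dose of study medication". Protocol 11.4.1 agrees: "All safety analyses will be performed using the safety population". Neither document makes an exception for the screening SAE table.

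**Data capture.** Protocol 12.1 says that CRFs "should be completed for each randomized subject". For screen failures, Protocol 9.2.2 asks for a log of disposition and reasons for ineligibility.

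**The concern.** The collection rule and the analysis population start at different points. Collection begins at consent, while membership of the table begins at the first dose. Everything the table is meant to show happens between those two points, and a subject harmed in that interval may never reach the second.

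The treatment-group columns add a second problem. All these events come before randomisation, so a split by later assignment cannot show a treatment effect. It only divides a small count across four groups.

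What is at stake is the description of harm from the pre-randomisation procedures, of which ESA withdrawal is the most demanding. A study report with a zero or near-zero row could be read as reassurance about screening procedures when the affected subjects were simply outside the table.

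**Working it through.** The plan states no figure here, so there is nothing to reproduce. The check is one of timing and population.

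**1. Order of events**
- Consent is signed at screening visit 1, and collection of procedure-related SAEs starts (Protocol 10.3.1).
- Subjects on ESAs then have 2, 4 or 8 weeks of washout between screening visits 1 and 2 (Protocol 8.4.2).
- Screening visit 3 follows for these subjects (Protocol 9.1).
- Randomisation takes place on Day 1, before dosing (Protocol 8.2.2).

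**2. Who can be in the table**
A subject needs a dose (SAP 4.8 and 4.4.1) and a treatment group (SAP 4.8.2). Neither exists before Day 1. A screening SAE is therefore counted only if the subject is later randomised and dosed.

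**3. Whether the omission is selective**
The protocol makes some serious events direct bars to entry:
- During screening (Protocol 7.3): red cell transfusion, severe heart failure, acute coronary syndrome, hospitalisation for heart failure, stroke, and DVT or PE needing active treatment.
- After screening visit 2 (Protocol 8.4.2): any ESA use.

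Being counted thus depends partly on the outcome being counted.

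**4. Whether another output recovers these subjects**
- The all-AE listing (SAP 4.8.2) includes non-treatment-emergent events but is also presented by treatment group.
- The partial-date rule (SAP 4.8.2) mentions undosed subjects. It shows that such records were foreseen, but it creates no output.
- The disposition summary (SAP 4.3.1) runs from screening but carries no SAE counts.
- The deaths listing (SAP 4.8.3) falls under the population rule in 4.8.
- A rescreened subject gets a new number at each attempt (Protocol 7.4.2). An SAE from a failed attempt can sit under a number that was never dosed, even if the person is later randomised.

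**5. What drives the size**
Let N be the persons consented, D those dosed, and e_D and e_U the numbers with such an SAE among dosed and undosed persons.
- The table shows e_D / D.
- The quantity of interest is (e_D + e_U) / N.
- The share of affected persons missing is e_U / (e_D + e_U).

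Only the planned D = 48 is in the documents (Protocol 6.1), taking all randomised subjects as dosed. If e_D = 0, the table reads zero for any e_U.

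The following is illustration only, with an assumed screen-failure share f and N = 48 / (1 − f), rounded up:

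| Assumed f | N | Outside the table |
|---|---|---|
| 20% | 60 | 12 |
| 30% | 69 | 21 |
| 50% | 96 | 48 |
| 60% | 120 | 72 |

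With f = 50% (48 dosed, 48 undosed) and assumed SAE risks:

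| Risk, undosed | Risk, dosed | True rate | Table rate | Share missing |
|---|---|---|---|---|
| 4% | 4% | (1.92 + 1.92)/96 = 4% | 4% | 50% |
| 6% | 2% | (2.88 + 0.96)/96 = 4% | 2% | 75% |
| 4% | 0% | (1.92 + 0)/96 = 2% | 0% | 100% |

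In the first row the count is halved but the percentage is right. The percentage is biased once risk is higher in those who drop out, which step 3 gives reason to expect.

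**The case against.** The case on the other side is substantial on scope.

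- **The events are not lost.** Under Protocol 10.3.3 every SAE goes to the sponsor or CRO within 24 hours, and the sponsor reports onward. The reporting period was changed for reporting purposes, and that aim is met. This stands: a reader might infer that washout harm goes unreported, and the documents do not support that.
- **Most affected subjects need not be lost to the table.** An SAE is not in itself an exclusion. Only named events, ESA use after screening visit 2 or investigator judgement exclude, and rescreening is possible in some cases. This also stands. A reader might infer that most of these events are missing, but no figure in the documents supports any particular share.
- **The table is not a washout table.** It covers any protocol procedure. In addition, Protocol 10.1.1 does not treat worsening anaemia as an AE unless it has a cause other than CKD. A corrected population would therefore still not show the most direct effect of ESA withdrawal. Both limits stand.
- **The shells may include a not-randomised column.** They are not available, so this cannot be ruled out. The SAP text as written gives no such column and no other denominator, and the sentence on separate tabulation names no population.
- **The consequence is small.** Safety analysis is descriptive (Protocol 11.7), and the primary endpoint and type I error are untouched. This is true, and it bears on priority rather than on whether the count is right.

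**Conclusion.** The point holds for the planned tabulation. As written, a procedure-related SAE during screening cannot enter the SAP 4.8.2 table if the subject is not then randomised and dosed, and no other defined output supplies it. Because some serious screening events themselves exclude the subject, the table can understate these events, possibly as zero.

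The size cannot be derived. It depends on the number consented and on how many affected subjects are never dosed, and the documents give neither. The conclusion rests on reading SAP 4.8 literally, as covering every safety summary. It should be corrected before the tables are produced. It does not affect expedited SAE reporting, efficacy or post-dose safety.

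**What to change.** In SAP 4.8.2:

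- Tabulate and list screening-period procedure-related SAEs for all consented subjects, in one total column rather than by treatment group, showing randomised versus not randomised.
- Use the number of consented subjects as the denominator, and count each person once by linking subject numbers across rescreening attempts.
- State that this table and listing are exempt from the safety-population rule in SAP 4.8.
- Ensure that SAE records for screen failures enter the study database, since Protocol 12.1 requires CRFs only for randomised subjects.

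A denominator of washout starters split by washout length is not advised. It would need ESA-washout data on every screen failure, including those without an SAE, and the protocol does not require that.

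The cost is one revised table shell and a data-entry instruction. The SAEs are already reported, and no design or efficacy element changes.

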4.8.3 Deaths, Serious Adverse Events, and Other Significant Adverse Events

Other significant AEs are those AEs reported as leading to withdrawal from study. The summaries of SAEs and AEs leading to withdrawal from study are described in [section 4.8.2](#).

A summary of the number and percentage of deaths during the study will be provided by treatment group.

A summary of the number and percentage of subjects Adverse Events Leading to Death by treatment group, severity, SOC and PT

A by-subject listing of all deaths that occurred during the study will be provided.

4.8.4 Clinical Laboratory Evaluation

4.8.4.1 Liver function abnormality

A summary of Liver function abnormality by visit will be provided by treatment group. Any subject with at least one of the following liver function abnormalities is summarized:

- ALT $\geq 2x$ and $< 3x$ ULN
- AST $\geq 2x$ and $< 3x$ ULN
- Bilirubin $\geq 2x$ and $< 3x$ ULN
- ALT $\geq 3x$ ULN
- AST $\geq 3x$ ULN
- Bilirubin $\geq 3x$ ULN

4.8.4.2 Serum and urine pregnancy tests

Serum pregnancy test for females of childbearing potential will be performed at the screening visit and will be used for subject’s inclusion / exclusion. Urine pregnancy test will be performed at the baseline visit and used for subject’s initiation of study drug. Additional pregnancy tests may be conducted during the study to establish the absence of

pregnancy based on the investigator's clinical judgment or as required by local regulations.

A by-subject listing of serum and urine pregnancy tests will be provided.

4.8.4.3 Coagulation tests

Coagulation tests will be performed at the baseline visit. The following variables will be analyzed.

- prothrombin time
- partial thromboplastin time
- international normalized ratio

A summary of baseline coagulation test results will be provided by treatment group.

A by-subject listing of coagulation tests will be provided.

4.8.4.4 Folate and vitamin B12

Folate and vitamin B12 tests will be performed at the screening visit and will be used for subject's inclusion / exclusion.

A by-subject listing of folate and vitamin B12 tests will be provided.

4.8.4.5 Complete Blood Count (CBC)

The following components of the CBC are described in Efficacy / PD analysis section.

- Hb
- Hematocrit
- RBC count
- Automated Reticulocyte Count (both absolute and percent).

The following components of the CBC will be analyzed:

- Mean Corpuscular Volume
- Mean Corpuscular Hb
- Mean Corpuscular Hb Concentration
- Red Cell Distribution Width
- White Blood Cell count with differential (neutrophils, bands, lymphocytes, monocytes, eosinophils, and basophils)
- Platelets

The following summaries will be provided:

- A summary of each component of the CBC by treatment group and time point
- A summary of the change from baseline in each component of the CBC by treatment group and time point

A by-subject listing of CBC will be provided by treatment group.

4.8.4.6 Hemoglobin

The following Hb analyses will be performed for safety analysis section:

- A summary of the number and percentage of subjects with Hb increase > 1.0 g/dL in any 2-week interval by treatment group

4.8.4.7 Chemistry

The following laboratory parameters will be analyzed:

- Sodium
- Potassium
- Bicarbonate
- Chloride
- Calcium
- Phosphorus
- Glucose
- Creatinine
- Blood Urea Nitrogen
- Creatine Phosphokinase
- Uric Acid
- Albumin
- Total Protein
- Total Bilirubin
- Alkaline Phosphatase
- Alanine Aminotransferase (ALT)
- Aspartate Aminotransferase (AST)
- Lactate Dehydrogenase
- Total cholesterol

The following summaries will be provided:

- A summary of Chemistry by treatment group and time point
- A summary of the change (absolute and percent) from baseline in Chemistry by treatment group and time point

A by-subject listing of Chemistry will be provided by treatment group.

4.8.4.8 C-reactive protein and Vascular Endothelial Growth Factor (VEGF)

The following summaries will be provided:

- A summary of C-reactive protein (CRP), VEGF and total cholesterol by treatment group and time point
- A summary of the change (absolute and percent) from baseline in CRP, VEGF and total cholesterol by treatment group and time point

The effect of treatment in terms of the change from baseline to Week 6 in CRP, VEGF and total cholesterol will be analyzed using ANCOVA. The statistical model will assess

the main effect of treatment, adjusted for baseline measurement. Three post-hoc pairwise comparison, i.e., placebo vs 150 mg, placebo vs 300 mg, and placebo vs 600 mg, will be done. Unadjusted ANOVA will be performed for sensitivity.

A by-subject listing of CRP and VEGF will be provided by treatment group.

4.8.4.9 Laboratory Abnormalities

A summary of the number and percentage of subjects experiencing abnormal values by selected laboratory parameter with over with over CTCAE v.4.0 grade 3, treatment group and period will be presented.

The following parameter will be analyzed:

- Albumin
- Alkaline Phosphatase
- Calcium
- Creatine Kinase
- Glucose
- Phosphate
- Potassium
- Protein
- Sodium
- Alanine Aminotransferase
- Aspartate
- Aminotransferase
- Bilirubin
- Leukocytes
- Lymphocytes
- Neutrophils
- Platelets
- Activated Partial
- Thromboplastin Time
- Prothrombin Time

4.8.5 Vital Signs, Physical Findings and Other Observations Related to Safety

4.8.5.1 Vital Signs and Dry Weight

The following variables of vital signs will be analyzed:

- Blood Pressure (Systolic / Diastolic)
- Heart Rate
- Respiratory Rate
- Body Temperature

A summary table of subjects with blood pressure measured values after baseline visit will be provided by treatment group (Note: two categories of potential outlier for systolic blood pressure are ≥ 160 mmHg and < 180 mmHg; ≥ 180 mmHg; two categories of

potential outlier for diastolic blood pressure are ≥ 100 mmHg and < 110 mmHg, ≥ 110 mmHg) as well as subjects with increment from baseline (Note: two categories of potential outlier for systolic blood pressure increasing from baseline are ≥ 20 mmHg and < 40 mmHg, ≥ 40 mmHg; two categories of potential outlier for diastolic blood pressure are ≥ 10 mmHg and < 20 mmHg, ≥ 20 mmHg).

A summary table of subjects with heart rate measured values after baseline visit (two categories of potential outlier: ≥ 100 beats/min and < 120 beats/min, ≥ 120 beats/min) will be provided by treatment group as well as subjects with increment from baseline (two categories of potential outlier: ≥ 20 beats/min and < 30 beats/min, ≥ 30 beats/min)

The following summaries will be also provided:

- A summary of each vital sign parameter and dry weight by treatment group and time point.
- A summary of the change (absolute and percent) from baseline in each vital sign parameter by treatment group and time point.

Any findings of treatment-emergent vital sign and dry weight abnormalities will be handled as adverse event and reported in AE tables / listings.

A plot showing the mean blood pressure over time within each treatment group. 95% CI of these means will be shown as error bar and sample size in each group at each time point will be shown.

A by-subject listing of vital sign parameter with reference ranges will be provided.

4.8.5.2 12-lead ECG

The following variables will be analyzed at the Baseline Visit:

- Heart rate
- PR interval
- QT interval
- QRS interval
- QTc (corrected)
- Overall result

A summary of each ECG parameter will be provided by treatment group.

A by-subject listing of 12-lead ECG results will be provided.

4.8.5.3 Physical Examination and Weight Assessment

Physical Examination and Weight Assessment will be performed at the Screening Visit and used for subject's inclusion / exclusion. Weight and height will be reported in demographic tables and listings.

4.8.6 Safety Monitoring (Independent Data Monitoring Committee [IDMC], Data Monitoring Committee [DMC], Data and Safety Monitoring Board [DSMB])

Not applicable. No change of study conduct based on preliminary analysis result is planned.

4.9 Other Analyses

4.9.1 PK Analysis

The following summary will be provided:

- The summary of pre-dose plasma concentrations of vadadustat and its metabolites at Week 4 Visit by treatment group.
- Box plots of pre-dose plasma concentrations of vadadustat and its metabolites at Week 4 Visit by treatment group.
- Dose-normalized box plots of pre-dose plasma concentrations of vadadustat and its metabolites at Week 4 Visit by treatment group.

Concentrations below the limit of quantification (BLQ) will be replaced by the 0 for the calculation of descriptive statistics. So concentration contains BLQ values are treated as 0 for all summary statistics except geometric mean and its related parameters.

By-subject listings of pre-dose plasma concentrations of vadadustat and its metabolites will be provided by treatment group.

4.9.2 Treatment-Emergent Outliers analysis

The purpose of this analysis is to identify the treatment Emergent outliers by each prescribed dose at each period. The definition of prescribed doses is the subjects with latest dose amount at planned visit when dose change. e.g. if at Week 2 with dose 600 mg and dose reduced to 450 mg at week 4, then visit of prescribed dose for VADA 450 was assigned to Week 4.

However, if subject had dose reduction on 150 mg or had interruption of study medication, the prescribed dose will be considered as 0 mg.

Only treatment-emergent outliers will be counted but outliers at the baseline and screening visits will be excluded.

The following summary will be provided:

- The summary of subjects with prescribed Dose by treatment group and time point
- The summary of subjects with prescribed Dose by Above/Within/Below the target Hb Range and treatment group

In addition, the below components will be analyzed by primary efficacy period and dose adjustment and maintenance period for all subjects and for subjects with non-elevated values at baseline:

- Non-elevated at baseline definition for each component

- Systolic Blood Pressure <140 mmHg
- Diastolic Blood Pressure <90 mmHg
- Heart Rate <100 bpm
- Potassium <4 mEq/L

The following component with following criteria will be applied.

- Systolic Blood Pressure
 - Any SBP ≥ 160 to <180 mmHg
 - Any SBP ≥ 180 mmHg
 - Any SBP increase from baseline ≥ 20 to <40 mmHg
 - Any SBP increase from baseline ≥ 40 mmHg
- Diastolic Blood Pressure
 - Any DBP ≥ 100 to <110 mmHg
 - Any DBP ≥ 110 mmHg
 - Any DBP increase from baseline ≥ 10 to <20 mmHg
 - Any DBP increase from baseline ≥ 20 mmHg
- Heart Rate
 - Any pulse ≥ 100 to <120 bpm
 - Any pulse ≥ 120 bpm
 - Any pulse increase from baseline ≥ 20 to <30 bpm
 - Any pulse increase from baseline ≥ 30 bpm
- Potassium
 - Any Potassium >5.5 to 6.0 mEq/L
 - Any Potassium >6.0 to 6.5 mEq/L
 - Any Potassium >6.5 mEq/L
 - Any Potassium increase from baseline >0.5 to 1.0
 - Any Potassium increase from baseline >1.0 to 1.5 mEq/L
 - Any Potassium increase from baseline > 1.5 mEq/L

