### **8.2.5 Study Drug Administration during the Dose Adjustment and Maintenance Period (Week 7 to Week16)**

Subjects who complete the primary efficacy period will enter the dose adjustment and maintenance period. Subjects receiving placebo will be switched to vadadustat at the Week 6 visit. Specifically, at the Week 6 visit, sites will collect all unused study drug tablets dispensed during the primary efficacy period. Each subject will then be provided with 1 bottle of vadadustat. Each subject will initially take the same number of tablets of study drug after the Week 6 visit as before the Week 6 visit. For example, subjects taking 2 tablets of study drug (vadadustat or placebo) prior to the Week 6 visit will initially take 2 tablets of vadadustat after the Week 6 visit.

Subsequently, study drug dose will be adjusted to achieve a target Hb of 10.0-12.0 g/dL based on central laboratory Hb results and dose adjustment guidelines described below. Dose adjustments will be based on central laboratory Hb results from study visits at Weeks 6, 8, 10, 12, and 14.

- Do not increase the dose more frequently than once within any given 4-week interval. For example, if a subject's dose was increased based on Hb results from the Week 6 visit and the subject remains below the Hb target, the next opportunity to further increase the dose would be based on Hb results from the Week 10 visit. Decreases in dose can occur more frequently. Avoid frequent dose adjustments.
- If the Hb has not increased by more than 0.5 g/dL above the baseline value after the first 6 weeks of treatment, increase the dose by 1 tablet.
- Increase the dose by 1 tablet every 4 weeks until Hb is above 10.0 g/dL (maximum dose is 4 tablets).
- If the Hb increases rapidly (eg, more than 1 g/dL in any 2-week period), reduce the dose by 1 tablet.
- If the Hb falls below 10.0 g/dL, increase the dose by 1 tablet.
- If the Hb exceeds 12.0 g/dL, reduce the dose by 1 tablet.
- If the Hb exceeds 13.0 g/dL, interrupt study drug until the Hb decreases to 12.5 g/dL or below and then resume dosing with 1 fewer tablet.
- If a dose adjustment is required to maintain Hb at the desired level, the dose adjustment is by 1 tablet.

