#### 9.4.5 Week 4 Visit

When possible, this visit should be scheduled in the morning due to the pre-dose PK evaluation. The morning dose of study medication should be held until after the pre-dose PK sample is drawn.

At the Week 4 visit, the following activities/procedures will be performed:

- Vital signs
- Dry weight
- Dialysis treatment review
- AE review
- Rescue therapy (ESA rescue and RBC transfusion) review
- Laboratory procedures:
  - CBC
  - Chemistry
  - Iron indices
  - Pre-dose PK sample
- Record date and time of the last dose of the study drug that was taken prior to the pre-dose PK sample
- Concomitant medication review
- Dispense study drug (as necessary)
- Subjects should be questioned regarding dosing compliance
- Review dosing instructions and remind subjects that they may be contacted by telephone to discuss dose reduction if central lab Hb result demonstrates excess Hb response

- If central lab Hb result demonstrates excess Hb response, contact subject for dose reduction ([Section 8.2.4](#))

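### SAP 4.9.2 labels the readings at a dose-change visit with the dose that followed them, so the Hb-range-by-dose table is partly sorted by its own outcome

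*SAP*

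**What the plan says.** SAP 4.9.2 sits under Other Analyses. Its stated aim is to "identify the treatment Emergent outliers by each prescribed dose at each period". The label is defined thus: "The definition of prescribed doses is the subjects with latest dose amount at planned visit when dose change". The example takes a subject on 600 mg at Week 2 who is reduced to 450 mg at Week 4: "then visit of prescribed dose for VADA 450 was assigned to Week 4". If a subject is reduced from 150 mg or "had interruption of study medication, the prescribed dose will be considered as 0 mg". One listed output is "The summary of subjects with prescribed Dose by Above/Within/Below the target Hb Range and treatment group". The section then sets outlier categories for systolic and diastolic pressure, heart rate and potassium. It states no rule for joining a reading to a dose other than the visit itself.

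The protocol fixes the order of events. Section 8.2.5 says: "Dose adjustments will be based on central laboratory Hb results from study visits at Weeks 6, 8, 10, 12, and 14". Its rules include "If the Hb exceeds 12.0 g/dL, reduce the dose by 1 tablet", interruption above 13.0 g/dL, and one more tablet below 10.0 g/dL up to a maximum of four. For Week 4, section 9.4.5 says: "If central lab Hb result demonstrates excess Hb response, contact subject for dose reduction". Under 8.2.4 and 8.2.5 the site calls the subject after the central result arrives.

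**The concern.** At a dose-change visit the sample comes first, the laboratory result second and the new dose third. Labelling the visit with the new dose credits the reading to a dose that the subject had not yet taken. In the Hb table the problem is worse than noise, because the reading itself decides which row it goes into: overshoot moves to a lower dose and undershoot to a higher one. A reader of the table would see overshoot listed against 0 mg that arose on active drug. With about 48 subjects, a few misplaced readings can change what a row appears to show.

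**Working it through.** There is no stated figure to reproduce. The check applies the SAP label to the protocol's own rules and then uses an illustrative simulation for size.

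**1. Order of events at a change visit.** Protocol 9.4.5 collects vital signs, CBC and chemistry at Week 4, holds that day's dose until the PK sample is drawn, and makes any reduction depend on the Hb from that visit. Protocol 9.4.6 has the first tablet from the new bottle taken the day after Week 6. The activity schedules in Appendices A and B tie dose reduction to the Hb results of Weeks 2 and 4, and dose adjustment to those of Weeks 6, 8, 10, 12 and 14. The readings at these visits therefore precede the change.

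**2. Label against dose taken, Weeks 6 to 14, with 8.2.5 followed.**

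| Reading | Dose taken | SAP label |
|---|---|---|
| Hb above 12.0, up to 13.0 g/dL | 600 mg | 450 mg |
| Hb above 12.0, up to 13.0 g/dL | 150 mg | 0 mg |
| First Hb above 13.0 g/dL of an excursion | any active dose | 0 mg |
| Hb below 10.0 g/dL that triggers an increase | 150, 300 or 450 mg | 300, 450 or 600 mg |
| Hb below 10.0 g/dL | 600 mg (already the maximum) | 600 mg |

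At these visits the 600 mg row keeps its own below-target readings, gains some from 450 mg, and holds no above-target reading.

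**3. What is not affected.** At Weeks 2 and 4, only a rapid rise or an Hb above 13.0 g/dL changes the dose (8.2.4), so an Hb of 12 to 13 g/dL without a rapid rise keeps its dose. Week 16 has no adjustment. Visits without a change, and later visits during a continuing hold, are labelled correctly.

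**4. Illustrative size.** The simulation followed 40,000 subjects under 8.2.4 and 8.2.5. Assumptions that are not in the documents: within-subject Hb SD of 0.30 to 0.45 g/dL, a typical slope of 2.25 to 4 g/dL per 1000 mg, and lognormal variation in sensitivity between subjects. The lower slope agrees with Protocol 11.2, which assumes 1.35 g/dL at 600 mg: 1.35 / 0.6 = 2.25 g/dL per 1000 mg, or 1.35 / 4 = 0.34 g/dL per tablet. Results for Weeks 8 to 14:

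| Setting | Readings relabelled | Hb >12 at 600 mg: taken / label | Hb <10 at 150 vs 600 mg, by dose taken | Hb <10 at 150 vs 600 mg, by SAP label |
|---|---|---|---|---|
| Base (SD 0.45, slope 2.25) | 31.9% | 0.8% / 0.0% | 60.7% vs 47.9% | 38.2% vs 64.4% |
| SD 0.30 | 21.3% | 0.6% / 0.0% | 42.0% vs 45.3% | 19.8% vs 57.7% |
| Slope 4 | 31.4% | 2.8% / 0.0% | 39.4% vs 31.7% | 22.0% vs 53.1% |

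In every setting, all readings above 13 g/dL fall under 0 mg by the SAP label, against 0 to 2.8% by dose taken. In trial terms the above-target counts are small: 48 subjects x 4 visits = 192 readings, and 0.8% of 192 is about 1.5 readings even if everyone took 600 mg throughout.

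**The case against.** The wording of 4.9.2 is loose. The example does not say why the dose fell at Week 4. Changes are made between planned visits, so they have to be mapped to one, and the SAP does not say in which direction. If a change prompted by the Week 2 Hb were recorded at Week 4, the 450 mg label would be right. Prescribed dose could also mean the dose ordered in response to the Hb, which would make a coherent prescribing record. The outlier paragraph specifies analysis by period, and dose appears only in the statement of aim.

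Part of this stands. The SAP never states the join outright, and the safety outliers are affected only where they are displayed by prescribed dose. But the definition uses the latest dose at the visit where the change occurs, the example places the reduction at Week 4, and the protocol has sites act on each result within days. A prescribing record would also not serve the stated aim of finding outliers by dose.

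A reader might go further in four ways that the documents do not support:

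- **That 600 mg can never show an above-target reading.** It can at Weeks 2, 4 and 16, and whenever an investigator uses the discretion in 8.2.5 to dose outside the guidelines.
- **That the safety tables are reversed.** Dose changes follow Hb, not blood pressure, heart rate or potassium. Misattribution at change visits follows from the rule; reversal does not.
- **That the starting-dose choice is at risk.** That question rests on the Week 6 change by randomized group (SAP 4.7.1 and 4.7.2.1). Excess Hb, target range, blood pressure, heart rate and chemistry are also tabulated by randomized group.
- **That the simulated percentages are estimates for this trial.** A run at about 0.55 g/dL per tablet, or 4 x 0.55 = 2.2 g/dL at 600 mg against the protocol's 1.35, put 5 to 9% of 600 mg readings above target by dose taken. The protocol's slope gives 0.8%.

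**Conclusion.** The point holds for the descriptive tables in SAP 4.9.2. On the natural reading of the definition and its example, readings at a dose-change visit are credited to a dose that had not yet started. For the Hb-range table the direction of the error follows from the dose rules and needs no simulation, provided that sites follow 8.2.5. For blood pressure, heart rate and potassium, the claim is misattribution only.

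The simulated 21 to 32% of Week 8 to 14 readings indicates that relabelling would be common, not how often it will occur. The primary ANCOVA, the linear regression and the by-randomized-group tables do not use this label. Nor would a better label turn the table into a dose-response display. Hb by current dose is confounded by Hb-driven titration: in the SD 0.30 setting, readings below 10 g/dL are slightly more frequent at 600 mg than at 150 mg even by dose taken. The change is worth making because the stated rule puts readings in the wrong row and is cheap to put right.

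**What to change.** In SAP 4.9.2:

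- Join each reading to the dose in effect up to that visit's sample.
- Apply a new dose, including 0 mg on interruption, only to readings taken after it starts.
- Change the example so that Week 4 counts under 600 mg and readings after the change count under 450 mg.
- If the prescribing response to each Hb is of interest, show the newly prescribed dose as a separate column or table.
- State whether the outlier categories are shown by dose as well as by period.
- Add a footnote that Hb by current dose reflects titration and is not a dose-response comparison.

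The cost is SAP wording and a one-visit shift in programming. No new data are needed, and no dosing rule or randomized comparison changes.
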